4.3. Prior and Concomitant Medications

All medications (including statin, non-statin LMT, CV, and Other) taken from the time of informed consent to the end of the study, including medications that were started before the study and are ongoing during the study, will be reported in Concomitant Medications CRF.

All medications will be dictionary coded using the World Health Organization-Drug Dictionary (WHO-DD) to both an anatomic category and a therapeutic category, with the version in effect at the time of the database lock. Drug names will be matched to respective Anatomical-Therapeutic-Chemical (ATC) classification, although a drug can be matched to more than one ATC classification (i.e. patients can be counted in several categories for the same medication).

Definitions for deriving prior medications, concomitant and post-treatment medications are described below, with the understanding that a given medication can be simultaneously classified both as a prior and concomitant medication.

- Prior medications are any medications the patient used within the time period between 3 months prior to the screening visit up to the day before first study treatment administration. Prior medications can be discontinued before first treatment administration or can be ongoing during the treatment phase.
- Concomitant medications are defined as any treatments received by the patient concomitantly with the study treatment, specifically from the first day of study treatment administration to the last day of study treatment +70 days. Concomitant medications do not include medications started during the post-treatment period.
- Post-treatment medications are those medications administered to the patient during the time period starting from 71 days after the last study treatment administration and ending when the patient terminates the study.

4.4. Patient Disposition

Patient disposition includes the description of patient status at major milestone decisions in the study, as well as the patient analysis populations.

For patient study status, the following milestone categories are defined below. For all categories of patients, percentages will be calculated using the number of randomized patients as the denominator, with two exceptions. Specifically, the two exceptions are for the screened and non-randomized categories, which will not have associated percentages shown.

- Screened patients: The total patient counts will only be shown for pre-randomization information, and percentages will not be provided
- Screen failure patients and reasons for screen failure: The total patient counts will only be shown for pre-randomization information. Non-randomized but treated patients (include if applicable): The total patient counts will only be shown for pre-randomization information, and percentages will not be provided
- Randomized patients
- Randomized but not treated patients and reason for not being treated (including patient's decision for treatment period discontinuation)
- Randomized and treated patients
- Patients complete 96 weeks of double-blind treatment period (at least 94 weeks of exposure and visit W96 performed)
- Patients completed the study treatment period (i.e. as collected on the End of Double Blind Treatment eCRF)
- Patients who did not complete the study treatment period and patient's decision for treatment period discontinuation (as per the End of Double Blind Treatment eCRF)
- Patients who discontinued study treatment by main reason for permanent treatment discontinuation (as per the End of Double Blind Treatment eCRF)
- Patients completed the study (i.e. as collected on the Study Completion eCRF)
- Patients who early terminated the study (as per the Study Completion eCRF)
- Patients who early terminated the study by main reason for early termination (as per the Study Completion eCRF)
- Patients who will participate in the Open Label Extension Study
- Status at last study contact

As defined in Section 3. of this document, the patient analysis populations are:

- Randomized population
- Safety Population (SAF)
- Primary Safety Population (PSAF)

- Intent-to-Treat Population (ITT)
- Modified Intent-to-Treat Population (mITT)
- The Anti-alirocumab Antibody Population (ADA)

4.5. Study Treatment Exposure and Compliance Variables

Study treatment exposure variables are listed below with associated definitions:

- Patient duration of study treatment exposure in weeks defined as: (last study treatment administration date +14 – first study treatment administration date)/7, regardless of intermittent discontinuations.
- The following categories will be used for treatment exposure intervals: ≥ 1 day and <4 weeks, ≥ 4 weeks and <8 weeks, ≥ 8 weeks and <12 weeks, ≥ 12 weeks and <16 weeks, ≥ 16 weeks and <20 weeks, ≥ 20 weeks and <24 weeks, ≥ 24 weeks and <28 weeks, ≥ 28 weeks and <32 weeks, ≥ 32 weeks and <36 weeks, ≥ 36 weeks and <40 weeks, ≥ 40 weeks and <44 weeks, ≥ 44 weeks and <48 weeks,, ≥ 92 weeks and <96 weeks, ≥ 96 weeks.
- The total number of study treatment injections by patient.
- Patients with up-titration are defined as up-titration according to IVRS/IWRS week 12 transaction with at least 1 injection of alirocumab 150 mg following up-titration decision.

Compliance will be assessed using the following variables with associated definitions:

- For each patient, the mean injection frequency for study treatment injections will be defined as the average number of days between 2 consecutive injections, that is: $(\text{last injection date} - \text{first injection date}) / (\text{number of injections} - 1)$ for patients receiving at least 2 injections.

All important and minor protocol deviations potentially impacting primary endpoint, randomization and drug-dispensing irregularities, as well as other deviations, will be collected and reviewed on an ongoing basis throughout the study as described in the Protocol Deviation Plan (PDP). Both monitoring-collected and programmatically derived deviations are listed and defined in the PDP.

4.6. Primary and Secondary Endpoints

4.6.1. Primary Neurocognitive Endpoint

The primary outcome measure is the change in CANTAB cognitive domain SWM strategy score (SWMS) from baseline to week 96. Two definitions will be provided for this endpoint, specifically:

- SWM strategy z-score change from baseline is defined for each patient as: week 96 SWM strategy z-score minus the patient's baseline SWM strategy z-score. The change from baseline SWM strategy z-score is used for the primary analysis evaluation of noninferiority. A lower score denotes better SWM function (ie, less impairment).
 - A patient's SWM strategy z-score at week 96 is defined as: (week 96 SWM strategy raw score minus the SWM strategy mean baseline score) divided by the SWM strategy baseline standard deviation. The SWM strategy mean baseline score and the SWM strategy baseline standard deviation are calculated using patients in both treatment groups (ie, Praluent and placebo).
 - The SWM strategy z-score at baseline is defined for each patient in the same manner as the calculation for the SWM strategy z-score at week 96, replacing the patient's week 96 raw score with the patient's baseline raw score.
- SWM strategy raw score change from baseline is defined for each patient as: week 96 SWM strategy raw score minus the patient's SWM strategy baseline score. The SWM strategy raw score change from baseline is provided descriptively for clinical interpretation of function at week 96. Lower change from baseline raw scores reflect better SWM performance (ie, less impairment).

The baseline SWM strategy score is the last score obtained before the first dose of study treatment. The SWM Strategy score at week 96 is the score obtained within the week 96 analysis window and during the treatment-emergent adverse event (TEAE) period. The TEAE period is defined as the time from the first double-blind study treatment injection up to 70 days after the last double-blind study treatment injection. The analysis window used to allocate a time point to a measurement is defined in Appendix 10.2 of this SAP.

4.6.2. Exploratory Neurocognitive Endpoint

Exploratory neurocognitive outcome measures to further assess neurocognitive function in the CANTAB domains are provided below for each patient:

- Paired Associates Learning (PAL) at week 96 defined as both a PAL z-score change from baseline and PAL raw score change from baseline, following the definitions and rules provided for the primary neurocognitive endpoint
- Reaction Time (RTI) at week 96 defined as both a RTI z-score change from baseline and RTI raw score change from baseline, following the definitions and rules provided for the primary neurocognitive endpoint
- SWM between-errors score (SWMBE) at week 96 defined as both an SWM between-errors z-score change from baseline and SWM between-errors raw score change from baseline, following the definitions and rules provided for the primary neurocognitive endpoint

- Global Composite score at week 96 change from baseline is defined as (the average of the following 4 measures at week 96: SWM strategy z-score, PAL z-score, RTI z-score, and the SWM between-errors z-score) minus the average of the same 4 z-score measures at baseline

4.6.3. Secondary Efficacy Variable

The secondary efficacy endpoints are provided below. For those efficacy endpoints described as percent change from baseline at a given visit, the definition is: 100 multiplied (post-baseline visit measurement – baseline measurement) divided by the baseline measurement.

The baseline measurements are the last values obtained before the first dose of study treatment.

The secondary efficacy endpoint at a given visit is the measurement obtained within the analysis window of the visit and during the main efficacy period. The main efficacy period is defined as the time from the first double-blind study treatment injection up to the upper limit of the week 96 analysis window.

All secondary efficacy endpoints (scheduled or unscheduled) may be used to provide a value for the efficacy endpoint, if appropriate, according to above definition.

- The percent change in calculated LDL-C, apolipoprotein (Apo) B, non-high-density lipoprotein cholesterol (non-HDL-C), and Total-C from baseline to weeks 12, 24, 48, 72, and 96
- The percent change in lipoprotein a [Lp(a)], HDL-C, triglyceride (TG), and Apo A-1 from baseline to weeks 12, 24, 48, 72, and 96
- The proportion of patients reaching LDL-C <70 mg/dL (1.81 mmol/L) at weeks 12, 24, 48, 72 and 96
- The proportion of patients reaching LDL-C <50 mg/dL (1.29 mmol/L) at weeks 12, 24, 48, 72, and 96

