6.2.3. Secondary Efficacy Endpoints

The secondary efficacy endpoints are provided below. For those efficacy endpoints described as percent change from baseline at a given visit, the definition is: 100 multiplied (post-baseline visit measurement – baseline measurement) divided by the baseline measurement.

The baseline measurements are the last values obtained before the first dose of study treatment.

The secondary efficacy endpoint at a given visit is the measurement obtained within the analysis window of the visit and during the main efficacy period. The main efficacy period is defined as the time from the first double-blind study treatment injection up to the upper limit of the week 96 analysis window.

All secondary efficacy endpoints (scheduled or unscheduled) may be used to provide a value for the efficacy endpoint, if appropriate, according to above definition. The analysis window used to allocate a time point to a measurement will be defined in the SAP:

- The percent change in calculated LDL-C, apolipoprotein (Apo) B, non-high-density lipoprotein cholesterol (non-HDL-C), and Total-C from baseline to weeks 12, 24, 48, 72, and 96
- The percent change in lipoprotein a [Lp(a)], HDL-C, triglyceride (TG), and Apo A-1 from baseline to weeks 12, 24, 48, 72, and 96
- The proportion of patients reaching LDL-C <70 mg/dL (1.81 mmol/L) at weeks 12, 24, 48, 72 and 96
- The proportion of patients reaching LDL-C <50 mg/dL (1.29 mmol/L) at weeks 12, 24, 48, 72, and 96

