7.3. Handling of Study Drug Discontinuation and Patient Withdrawal from the Study

7.3.1. Study Drug Discontinuation

Study drug should be continued whenever possible. In the event study drug dosing is stopped, it should be determined if the stop can be made temporarily. Permanent discontinuation should be a last resort. In any case, the patient should remain in the study as long as possible.

Patients who prematurely discontinue study drug should remain in the study and undergo all study visits and procedures, with the exception of dosing with study drug. At the time of study drug discontinuation, the patient should have, as soon as possible, an unscheduled visit with the assessments that are normally done at the end of study (EOS) visit (this should take place within 5 days of discontinuation of study drug, if possible), and then resume the original study schedule until end of study.

Assessment of patients who do not consent to remain in the study after discontinuation of study drug should be managed according to Section [7.4.1](#).

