9.3.2.2. Modified Intent-to-Treat

The modified intent-to-treat (mITT) population (also known as the full analysis set) is defined as the all randomized population who took at least 1 dose or part of a dose of study drug and have an evaluable secondary efficacy endpoint. The endpoint is considered as evaluable when both of the following conditions are met:

- Availability of at least 1 measurement value for calculated LDL-C before first dose of study drug (ie, baseline)
- Availability of at least 1 calculated LDL-C value during the efficacy treatment period and within 1 of the analysis windows up to week 96; the efficacy treatment period is defined as the time from the first double-blind study drug injection up to 21 days after the last double-blind study drug injection

Patients in the mITT population will be analyzed according to the treatment group allocated by randomization.

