3.2.2. Modified Intent-to-Treat Population

The modified intent-to-treat (mITT) population is defined as the all randomized population who took at least 1 dose or part of a dose of study drug and have an evaluable secondary efficacy endpoint. The endpoint is considered as evaluable when both of the following conditions are met:

- Availability of at least 1 measurement value for calculated LDL-C before first dose of study drug (ie, baseline)
- Availability of at least 1 calculated LDL-C value during the efficacy treatment period and within 1 of the analysis windows up to week 96; the efficacy treatment

period is defined as the time from the first double-blind study drug injection up to 21 days after the last double-blind study drug injection

Patients in the mITT population will be analyzed according to the treatment group allocated by randomization.

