4.7.1. Adverse Events Variables

The period of safety observation starts from the time when the patient gives informed consent and continues into the following periods:

- The PRE-TREATMENT period: defined as the time from the signed informed consent up to the first study treatment injection.
- The treatment-emergent adverse event (TEAE) period: defined as the time from the first study treatment injection up to the day of the last study treatment injection + 70 days (10 weeks), as residual effect of Praluent is expected until 10 weeks after last dose of study treatment.

The TEAE period will include:

- The TREATMENT period is defined as the time from the first study treatment injection up to the day of last study treatment injection + 21 days, as serum concentration of alirocumab >10 µg/mL is expected for approximately 21 days following administration of 150 mg. Further, in previous studies, alirocumab concentrations declining below this concentration also showed a decrease in effect on LDL-C.
- The RESIDUAL TREATMENT period is defined as the time from the day of last study treatment injection + 22 days up to the day of last study treatment injection + 70 days (10 weeks).
- The POST-TREATMENT period: defined as starting the day after the end of the TEAE periods (i.e., 71 days after the last study treatment injection) up to the patient's end of study.

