5.6.3. Analyses of Secondary Efficacy Variables

For secondary efficacy endpoints of lipids (defined in Section 4.6.3), descriptive summaries and analyses will be performed in the ITT population (for ITT analysis) and the mITT population (for on-treatment analysis). P-values for the testing of study treatment effect will be provided for descriptive purposes only (nominal p-values).

For descriptive summaries, percent change from baseline in calculated LDL-C, Total-C, HDL-C, TG, non-HDL-C, Apo B, Apo A-1, and Lp(a) will be provided at each time point for each treatment group. All measurements, scheduled or unscheduled, will be assigned to analysis windows defined in the SAP in order to provide an assessment for these time points. Laboratory assessments other than the ones provided by the central laboratory will be excluded. The time profile of each parameter will be plotted by treatment group with the corresponding standard errors. For TG and Lp(a), summary statistics will include Q1 and Q3.

Multiple types of measurements are planned to be analyzed during the trial, specifically continuous measurements expected to have a normal distribution (eg, percent change in calculated LDL-C), continuous measurements expected to have a non-normal distribution (eg, TG), and binary measurements (eg, proportion of patients reaching LDL-C <70 mg/dL).

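### No rule limits the mITT on-treatment lipid analysis to on-treatment values: the 21-day period selects patients, not measurements

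*SAP*

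**What the plan says.** **Endpoint definition.** SAP 4.6.3 and protocol 6.2.3 define the lipid endpoints once, with no split by analysis population. A value counts for a visit if it was "obtained within the analysis window of the visit and during the main efficacy period". On the period itself: "The main efficacy period is defined as the time from the first double-blind study treatment injection up to the upper limit of the week 96". SAP Appendix 10.2, Table 3, puts the end of that window at study day 756. The date of the last injection plays no part.

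**Populations and labels.** SAP 5.6.3 and protocol 9.5.2.3 name two lipid analyses. One is in the ITT population, the other in "the mITT population (for on-treatment analysis").

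**Where the 21 days appear.** Besides a baseline LDL-C and at least part of one dose, SAP 3.2.2 requires for mITT: "Availability of at least 1 calculated LDL-C value during the efficacy treatment period and within 1 of the analysis windows up to week 96". In protocol 9.3.2.2, "the efficacy treatment period is defined as the time from the first double-blind study drug injection up to 21 days after the last double-blind" injection. This is an entry condition for patients.

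**Why 21 days matter.** SAP 4.7.1 explains its 21-day treatment period by drug concentration and adds that in previous studies "alirocumab concentrations declining below this concentration also showed a decrease in effect on LDL-C". It expects residual effect until 10 weeks after the last dose.

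**Follow-up after stopping.** Protocol 7.3.1: "Patients who prematurely discontinue study drug should remain in the study and undergo all study visits and procedures", dosing excepted.

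**The concern.** The label and the endpoint definition do not match. One on-treatment LDL-C value admits a patient to mITT, and no rule then removes that patient's later values. A programmer working from the endpoint definition would keep lipid values measured months after the last injection. A programmer working from the label would drop them. The SAP exists to settle such choices before unblinding.

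A secondary objective is the effect of Praluent on lipoproteins, and the plan offers both an ITT and an on-treatment answer. Under the literal reading the second answer is close to a repeat of the first. Any off-drug values in the Praluent arm pull it toward placebo, both for percent changes and for the proportions below 70 and 50 mg/dL.

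**Working it through.** **1. The plan's own figures.** The documents give no expected lipid effect and no drug-stopping rate. The nearest figure is the sample-size dropout in SAP 2.2 and protocol 9.2: 20% in year 1 and 25% in year 2. Retention is 0.80 × 0.75 = 0.60, and 651 / 0.60 = 1085 per group, as stated. Planned cumulative dropout is therefore 40%. That is loss to the primary analysis, not drug stopping, so it serves below only as the outer end of a range.

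**2. Which values each analysis admits.**
- Primary endpoint (SAP 4.6.1): in the visit window and within the TEAE period, last injection + 70 days.
- LDL-C below 25 or 15 mg/dL (SAP 4.8): within the treatment period, last injection + 21 days.
- By-visit laboratory and vital-sign summaries (SAP 5.7.2, 5.7.3): up to last dose + 21 days.
- Lipid endpoints (SAP 4.6.3): in the visit window, up to day 756.
- MMRM, robust regression, logistic regression with its LOCF fallback, and by-visit summaries (SAP 5.6.3.1 to 5.6.3.4): run in both lipid populations, with no further limit on values.

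So the SAP writes a cut-off on values where it wants one. For lipids it names a period, and that period is the one that suits ITT.

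**3. Day arithmetic** (a dose at week w falls on day 7w + 1; visit days from Appendix 10.2, Table 3).
- *Completer.* Last dose at week 94 = day 659; on treatment to 659 + 21 = 680. The scheduled week 96 visit, 673 ± 7 = days 666 to 680, is on treatment.
- *Last dose at week 6.* Day 43; on treatment to day 64. The week 8 value (day 57) admits the patient to mITT. Values at weeks 12, 24, 48, 72 and 96 fall 42, 126, 294, 462 and 630 days after the last dose, and all count. Four of the five lie beyond the 70-day residual period.
- *Last dose at week 46.* Day 323; on treatment to day 344. The week 72 and 96 values, at 182 and 350 days, count.
- *General.* A scheduled week 96 value (day 673) is off treatment if the last dose was on or before day 673 − 22 = 651. For week 12 (day 85) the limit is day 63. Late visits are therefore far more exposed than early ones.

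**4. Dilution.** Let D be the true on-treatment difference, f the share of Praluent-arm mITT values at a visit that are off drug, and r the share of the effect remaining off drug. The estimated difference is about D × [1 − f(1 − r)].

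| f | r = 0 | r = 0.25 |
|---|---|---|
| 0% | 1.00 D | 1.00 D |
| 5% | 0.95 D | 0.9625 D |
| 10% | 0.90 D | 0.925 D |
| 20% | 0.80 D | 0.85 D |
| 40% | 0.60 D | 0.70 D |

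Both f and r are assumptions. The row f = 40% is the extreme in which all planned dropout is drug stopping with full attendance afterwards. The formula is for a difference in means. Odds ratios and robust-regression estimates should move the same way, but not by exactly these factors. Limiting values to last injection + 21 days sets f = 0, so the analysis targets D, given its missing-data assumption.

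**The case against.** The strongest reply is that the sponsor probably meant to apply a cut-off. The on-treatment label and a named 21-day period point that way, and no sentence says outright that post-washout values enter mITT. That stands, so one cannot say the sponsor chose to include them. But the only written rule on values admits them, and nothing in SAP 5.6.3 to 5.6.3.4 overrides it.

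Three stronger readings are tempting, and the documents do not support them:
- *The on-treatment effect will be understated.* This depends on stoppers returning for lipid tests. If those who stop drug also leave the study, dilution is close to nil.
- *The size follows from the planned 20% and 25% dropout.* Those rates do not separate stopping drug from leaving the study, and no lipid effect is stated.
- *The plan gives the ITT answer twice.* mITT drops untreated patients and those with no on-treatment LDL-C value in a window, so the two analyses nearly coincide but are not identical.

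It is also fair to say that the stakes are limited. Lipid p-values are nominal (SAP 5.6.3, 5.6.4), and a bias toward no effect would not create a false lipid benefit.

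**Conclusion.** The concern holds on the text as written. The efficacy treatment period governs membership of mITT and nothing else, so off-drug values in patients who stop early and keep attending would be analysed as on-treatment. The bias runs toward no effect, assuming the lipid effect fades after stopping, as SAP 4.7.1 indicates.

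Its size cannot be fixed from the documents. With no effect left off drug, it ranges from none to a loss of 40% of the true difference as the off-drug share goes from 0% to 40%. It is smaller at early visits, or where some effect persists. Scheduled week 96 values of patients dosed to week 94 are not affected.

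The consequence is confined to the secondary mITT lipid results. The primary analysis has its own TEAE-period limit, and the ITT lipid analysis properly uses the main efficacy period. The gap should be closed before unblinding.

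**What to change.** In SAP 4.6.3 and 5.6.3, state that:
- the ITT analysis uses values in the visit window and within the main efficacy period;
- the mITT analysis uses only values in the visit window and within the efficacy treatment period, from first injection to last injection + 21 days;
- for mITT, later values are set to missing before the MMRM, multiple imputation, the LOCF fallback and the by-visit summaries.

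Apply the date filter before SAP 6.5 picks the value nearest the target day. Otherwise a nearer off-drug value could displace an on-treatment one in the same window. Align protocol 6.2.3 and 9.5.2.3, or record the departure in SAP 1.2.3, which now lists none.

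The cost is a few sentences and one date filter, with no change to data collection or conduct. The downside is fewer mITT values at late visits, so the on-treatment estimate there leans more on the missing-data assumption.
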